## PROTOCOL CHANGE HISTORY

Version	Section(s)	Page(s)	Description of Change(s)	Rationale for Change(s)
1.0	N/A	N/A	Original	N/A
2.0	Personnel and Facilities	6	Updated contact information	Changes reflect a change in personnel and contact information
	Appendix A and C	44 and 47	Removal of Pentacam and Humphreys	Allow use of any type of topographer

## 1. SYNOPSIS

PROTOCOL:	A prospective study to evaluate the feasibility of a new treatment algorithm to increase depth of focus after wavefront-guided LASIK correction of myopic refractive errors with the iDesign Advanced Wavescan Studio™ System and Star S4 IR™ Excimer Laser System.
PROTOCOL NUMBER:	STAR-116-TOPS
STUDY TREATMENTS:	Investigational Product: iDesign 1.3-PRESBY treatment  Control Product: iDesign Advanced Wavescan Studio™ System (software version 1.3)
STUDY OBJECTIVE:	The purpose of this study is to determine whether wavefront-guided LASIK correction of myopic refractive errors with CustomVue combined with iDesign 1.3-PRESBY (presbyT-LASIK) treatments mitigate the effects of presbyopia by increasing the depth of focus compared to iDesign CustomVue treatments.
CLINICAL HYPOTHESIS:	The results of this study will demonstrate that wavefront-guided LASIK correction of myopic refractive errors with presbyT-LASIK treatments provide improved distance corrected intermediate visual acuity (at 67 cm) and improved distance corrected near visual acuity (at 40 cm) compared to iDesign CustomVue treatments thus reducing symptoms of presbyopia. Additionally, best corrected distanced visual acuity will be maintained with presbyT-LASIK treatments.

## OVERALL STUDY DESIGN:

Structure:	Prospective, multi-center, non-randomized, contralateral, open-label, clinical study.
Number of sites:	Up to 4 sites in Canada
Duration:	9 months
Definitions:	PresbyT-LASIK is defined as the iDesign 1.3-PRESBY Treatment Planning Software, test treatment.  iDesign CustomVue is the iDesign Advanced WaveScan Studio™ System (software version 1.3), control treatment.
Administration:	Surgeons will perform wavefront-guided LASIK for the treatment of myopic refractive errors based upon

measurements obtained with the iDesign System using the STAR S4 IR™ laser and PresbyT-LASIK.

**Visit Schedule:** There will be 10 scheduled study visits: preoperative, contact lens dispense, contact lens follow-up, operative, 1-day, 1-week, and 1, 3, 6 and 9 months.

## STUDY POPULATION CHARACTERISTICS:

**Condition:** Stable myopic refractive error with and without astigmatism and presbyopia.

**Number of Subjects:** Up to 70 subjects will be enrolled to achieve up to 34 treated subjects. Both eyes of subjects will be treated in the study. The control eye will receive the iDesign CustomVue treatment, test eye will receive the PresbyT-LASIK.

Each site should enroll a minimum of 10 subjects.

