## **4. STUDY DESIGN**

This study is a 9 month, prospective, multicenter, non-randomized, contralateral, open-label clinical study.

The study will be conducted at up to 4 sites in Canada and will include up to 34 test group treated eyes (of up to 34 subjects). Subjects must have both eyes treated in the study. The dominant eye will be treated with the control product; the non-dominant eye will be treated with test product. Analyses will be conducted at 6 months.

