## **8. STUDY POPULATION**

All study subjects will be enrolled from the normal myopic patient population at up to 4 sites in Canada. Up to 70 subjects will be enrolled to achieve at least 34 subjects at the 6 month postoperative visit. Each site should treat a minimum of 10 subjects.

This study will include only subjects who will undergo bilateral myopic and myopic astigmatic iDesign CustomVue treatments. The non-dominant eye will receive the PresbyT-LASIK treatment.

All subjects who meet the inclusion/exclusion criteria will be offered enrollment in the study. Eligibility criteria may not be waived by the investigator. Any questions regarding patient eligibility are to be discussed with AMO prior to subject enrollment. Subjects will be enrolled until the recruitment goals are met.

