## **10. EXPERIMENTAL PLAN**

### **10.1 OVERVIEW**

This study will be conducted in accordance with Health Canada Medical Devices Regulations, the Declaration of Helsinki, ISO 14155 and all other applicable laws and regulations. The study will not begin until regulatory and IRB approvals have been obtained.

This study will be prospective, multicenter, non-randomized, contralateral, open-label clinical investigation conducted at up to 4 sites. Up to 70 subjects will be enrolled to achieve approximately 34 treated subjects at 6 months. After signing the informed consent, completing the contact lens study, and meeting all inclusion and exclusion criteria in both eyes, the subjects may then be scheduled for surgery. The follow-up visit schedule will be the same for both eyes, as described in Section 10.2, Visit Schedule.

To maintain consistency, it is recommended that a single individual (study technician or coordinator designated by the investigator) conduct all study-related vision testing at each site, although a back-up person should also be designated and trained.

Key data collection for all subjects/eyes includes distance visual acuities, manifest refraction, iDesign measurements, keratometry, corneal topography, visual symptoms, biomicroscopic slit-lamp findings, complications and adverse events. A chart summary of all examination procedures required at each study visit is provided in **Appendix A**. Specific equipment necessary to perform the required procedures will be supplied for the duration of the study as noted in **Appendix B**.

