## 10.3 PREOPERATIVE PROCEDURES

All subjects enrolled in the study must sign the current IRB approved informed consent document and meet the inclusion/exclusion criteria. The informed consent must be signed before any study-specific examinations are performed, and this must be documented in the source documents. An Authorization for medical treatment privacy law documentation must also be signed.

All preoperative testing for the study must be completed within 120 days prior to surgery. Following the informed consent process, completion of the preoperative study exam,

completion of the contact lens trial and determination that the subject's eyes meet all of the required entrance criteria, the eyes may be treated in the study.

*As the Informed Consent Form is signed at the beginning of the preoperative study exam, some subjects may not qualify after study-specific testing is performed. Subjects will be considered screen-failures if they do not qualify or if they qualify but decide not to proceed with surgery. These subjects will be exited from the study.*

The following preoperative procedures are to be performed (see also **Appendix A**). General descriptions and requirements of the various tests are provided in the manual of testing procedures (**Appendix C**).

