#### **20.6 SAMPLE SIZE CALCULATIONS**

The sample size determination is based on intermediate visual acuity. There is over 80% power to detect a 0.7 line or greater difference in mean visual acuity between the test and control eyes with 34 subjects. This assumes a two-sided paired t-test with an alpha of 0.05 and standard deviation of 1.4 lines.

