4 SAMPLE SIZE CALCULATIONS

The sample size determination is based on intermediate visual acuity. There is over 80% power to detect a 0.7 line or greater difference in mean visual acuity between the test and control eyes with 34 subjects. This assumes a two-sided paired t-test with an alpha of 0.05 and standard deviation of 1.4 lines.

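### The target of 34 is a ceiling on treated subjects in two places, a floor at 6 months in a third and approximate in a fourth, so the study-level stopping point is ambiguous and, under the ceiling, the stated power has no allowance for loss

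*Protocol*

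**What the plan says.** Four places in the protocol define the target.

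- Synopsis, Number of Subjects: "Up to 70 subjects will be enrolled to achieve up to 34 treated subjects". This is a maximum, counted at treatment.
- Section 4: the study "will include up to 34 test group treated eyes (of up to 34 subjects". The same maximum.
- Section 8: "Up to 70 subjects will be enrolled to achieve at least 34 subjects at the 6 month postoperative visit". This is a minimum, counted at follow-up.
- Section 10.1: "Up to 70 subjects will be enrolled to achieve approximately 34 treated subjects at 6 months". Neither maximum nor minimum, counted at 6 months.

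The site minimum of 10 also varies: the Synopsis applies it to subjects enrolled, Section 8 to subjects treated. The Synopsis allows up to four sites.

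Protocol 20.6 claims "over 80% power to detect a 0.7 line or greater difference in mean visual acuity between the test and control eyes with 34 subjects", and adds: "This assumes a two-sided paired t-test with an alpha of 0.05 and standard deviation of 1.4 lines". SAP Section 4 makes the same claim: "There is over 80% power to detect a 0.7 line or greater difference in mean visual acuity". The primary analysis is a paired t-test at 6 months, one-sided at 0.025. Neither document states an assumed loss rate or describes imputation.

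**The concern.** The four statements differ in direction (maximum, minimum, approximate) and in what they count (subjects treated, or subjects present at 6 months). They give different answers to one study-level question: once 34 subjects have been treated, does treatment stop, or does it continue until 34 have reached 6 months?

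The answer matters for the power claim because a paired test uses only subjects with a 6-month value in both eyes. On the Synopsis and Section 4 wording, the 70 enrolled cover only attrition before surgery. Section 10.3 says: "Subjects will be considered screen-failures if they do not qualify or if they qualify but decide not to proceed with surgery". They add no treated pair beyond 34. On the Section 8 wording, the 70 could also cover losses after surgery. At stake are the number of subjects who have surgery and whether the planned power describes the data the study will have.

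**Working it through.** **1. Can the statements hold together?** Let T be the number treated and E the number seen at 6 months, so E ≤ T. The Synopsis and Section 4 give T ≤ 34. Section 8 gives E ≥ 34. Together, 34 ≤ E ≤ T ≤ 34, so T = E = 34: exactly 34 treated and no loss.

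**2. Site minimum.** Section 8 read literally at four sites: 4 × 10 = 40 treated, above 34. At three sites, 3 × 10 = 30, which fits. The Synopsis version (enrolled, with 70 available) has no such conflict.

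**3. Reproducing the stated power.** Inputs from Protocol 20.6 and SAP 4: difference 0.7 line, SD 1.4 lines, n = 34, paired t-test, two-sided alpha 0.05. Assumption: 1.4 is the SD of the paired difference, which the text does not say. Power is the probability that a noncentral t variable with n − 1 degrees of freedom and noncentrality (0.7/1.4) × √n falls beyond the critical t value. For n = 34 the noncentrality is 0.5 × √34 = 2.915 and the power is 0.8078. The one-sided 0.025 test named for the analysis gives the same to four decimals. The stated figure is reproduced.

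**4. Fewer complete pairs, same formula.**

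| Complete pairs | Power at 0.7 line | Power at 1.0 line |
|---|---|---|
| 34 | 80.8% | 98.1% |
| 33 | 79.5% | 97.8% |
| 32 | 78.2% | 97.5% |
| 31 | 76.8% | 97.0% |
| 30 | 75.4% | 96.6% |

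With the named test and the stated inputs, 34 is the smallest number that exceeds 80%. The one-line column uses the clinical threshold in Section 6.1.

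**5. Illustrative loss.** The documents give no rate, so these are assumptions. With 34 treated and independent losses, power averaged over the binomial number of remaining pairs is 78.6% at 5% loss, 76.2% at 10% and 73.5% at 15%. The chance of losing no pair is 0.95^34 = 17%, 0.90^34 = 2.8% and 0.85^34 = 0.4%.

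**6. If 1.4 were a per-eye SD.** The SD of the difference would be 1.4 × √(2(1 − r)), where r is the between-eye correlation. At r = 0.5 this equals 1.4 and nothing changes. At r = 0.3 it is 1.657, and 34 pairs give 66.7%. At r = 0.6 it is 1.252, and 34 pairs give 88.6%. These correlations are also assumptions. They show why the SD should be labelled; they are not evidence about the target of 34.

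**The case against.** Several points on the other side have force.

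- **Rounding.** The SD is given to one decimal. An SD of 1.38 also rounds to 1.4 and gives 80.7% with 33 pairs. A true difference of 0.72 line gives 81.7% with 33. By normal approximation, ((1.960 + 0.842) × 1.4/0.7)² = 31.4, so 32 pairs would do. The 1.2-point drop from one lost pair is therefore within the precision of the inputs. This stands as a limit on size. It does not supply an allowance for loss, and the plan names a t-test.
- **Section 8 already has a workable target.** At least 34 at 6 months agrees with the power statement. True, but the Synopsis and Section 4 contradict it.
- **Retention is planned.** Section 10.8 asks for every effort at complete follow-up and Section 15.1 covers prevention of missing data. SAP 3.1 provides for counting missed, lost or discontinued eyes, but that is a routine accountability table, not a forecast of attrition. It also counts out-of-interval eyes as available, so a late visit need not cost a pair.
- **It is a feasibility study.** A formal loss rate is less pressing here than in a confirmatory trial.

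A reader might infer that individual sites would diverge, one halting at 34 while another carries on. The documents do not support that: 34 is a total for the whole study across up to four sites, and Section 8 ties the end of enrolment to recruitment goals being met. A reader might also infer that the study is underpowered. That does not follow either, since power stays near 97% at the one-line threshold with 30 or 31 pairs.

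**Conclusion.** The contradiction stands in the current text. The target is a study-wide ceiling on treated subjects, a floor at 6 months and an approximate number at 6 months, and the treated-per-site minimum exceeds the ceiling if all four sites are used. The point at which treatment stops is therefore ambiguous.

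On power, the conclusion is conditional. If 1.4 lines is the SD of the paired difference, and the ceiling of 34 treated applies, the claim of over 80% at 0.7 line is met by 34 complete pairs with nothing to spare. About 10% loss would bring it to roughly 76% or 77%. To say without qualification that the claim fails once any pair is lost would go too far, because it depends on an unlabelled SD quoted to one decimal. The practical effect is modest, and the endpoint, hypotheses and test are untouched. The text should still be corrected, because it governs how many subjects have surgery.

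**What to change.** Use one study-level definition of 34 in the Synopsis and Sections 4, 8 and 10.1.

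- **If the ceiling on treated subjects is kept:** change Sections 8 and 10.1 to match, change the Section 8 site minimum so that it fits under the ceiling with four sites, and restate power in Protocol 20.6 and SAP 4 at the expected number of complete pairs. For example: about 77% with 31 pairs at 0.7 line, naming the assumed loss of about 10% (34 × 0.90 = 30.6). This is wording only. The cost is a slightly less favourable power figure.
- **If at least 34 at 6 months is what the sponsor already intends:** remove the ceiling from the Synopsis and Section 4 and align Section 10.1. This may mean a few more subjects having bilateral surgery: at an assumed 10% loss, 34/0.90 = 37.8, so about 38 treated. That fits within 70 enrolled if at least 38/70 = 54% reach surgery; the documents give no expected screen-failure rate. The added exposure has to be weighed against Section 2, which reports no clinical studies of this planning software, though it cites a retrospective study of ablations with the algorithm.

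In either case, use the same verb for the site minimum in the Synopsis and Section 8, and state in Protocol 20.6 and SAP 4 whether 1.4 lines is the SD of the paired difference.

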### Inclusion Criteria (all criteria apply to each eye):

1. Signed informed consent and Personal Health Information Protection Act authorization.
2. At least 45 years of age at enrollment (date informed consent signed).
3. The refractive error, based on the iDesign displayed refraction selected for treatment (“4.0 Rx calc” at 12.5 mm), must be myopia with or without astigmatism with sphere up to -6.00 D, and cylinder between 0.00 D and -5.00 D with a maximum spherical equivalent (SE) of -8.00 D.
4. Require an add power of +1.00 D or more during near testing at 40 cm.
5. Anticipated stromal bed thickness of at least 250 microns based on preoperative central corneal pachymetry minus the maximum ablation depth (as calculated by the iDesign system) plus the intended flap thickness.
6. Distance Best Spectacle Corrected Visual Acuity (BSCVA) of 20/20 or better.
7. Uncorrected Visual Acuity (UCVA) of 20/40 or worse.
8. Less than or equal to 0.75 D difference between cycloplegic and manifest refraction sphere.
9. A stable refractive error (based on a previous exam, medical records, lensometry, or prescription at least 12 months prior to the preoperative manifest refraction), as defined by a change of  $\leq 1.00$  D in MRSE.
10. Any eye with a history of contact lens wear within the last 4 weeks must demonstrate refractive stability according to the following:
  - o Rigid contact lenses (toric or spherical) must be removed for at least 4 weeks and soft contact lenses (toric or spherical) for at least 2 weeks prior to the first refraction used to establish stability.

- Two consecutive refractions and keratometric readings must be conducted at least 7 days apart.
- Refractive stability is defined as a change of not more than 0.50 D in manifest refraction sphere and cylinder as well as mean keratometry between measurements.
- If the subject/eye meets the refractive stability criteria, contact lens wear is not permitted prior to surgery.

11. Agreement between manifest refraction (adjusted for optical infinity) and iDesign System refraction selected for treatment, as follows:

- Spherical Equivalent: Magnitude of the difference is less than 0.625 D.
- Cylinder: Magnitude of the difference is less than or equal to 0.5 D.
- Cylinder Axis Tolerance: If either the manifest cylinder entered into the iDesign System or the iDesign cylinder selected for treatment is less than 0.5 D, there is no requirement for axis tolerance. When both cylinders have a magnitude of at least 0.5 D, the axis tolerance as determined by the iDesign system is linearly reduced from 15° (0.5 D) to 7.5° (7.0 D) based on the average magnitude of both cylinders. Note: If the axis tolerance is not in the calculated range, the iDesign system will produce a warning and this exam may not be used for treatment planning.

12. Willing and capable of complying with follow-up examinations for the duration of the study.

**Exclusion Criteria (all criteria apply to each eye):**

1. Women who are pregnant, breast-feeding, intend to become pregnant, or are not using an adequate method of birth control [examples are any form of barrier contraception (such as condom or diaphragm with contraceptive cream/jelly), birth control pills, hormonal implant, IUD, abstinence or surgical sterilization (tubal ligation, hysterectomy or vasectomy)]. Note: Women who were pregnant or nursing may not be enrolled until 6 months after either delivery or have stopped nursing and there is documented refractive stability.
2. Concurrent use of systemic (including inhaled) medications that may impair healing, including but not limited to: antimetabolites, isotretinoin (Accutane®) within 6 months of treatment, and amiodarone hydrochloride (Cordarone®) within 12 months of treatment.

**NOTE: The use of inhaled or systemic corticosteroids, whether chronic or acute, is deemed to adversely affect healing and subjects using such medications are specifically excluded from eligibility.**

3. History of any of the following medical conditions, or any other condition that could affect wound healing: collagen vascular disease, autoimmune disease, immunodeficiency diseases, ocular herpes zoster or herpes simplex, endocrine disorders (including, but not limited to unstable thyroid disorders and diabetes), lupus, and rheumatoid arthritis.

**NOTE: The presence of diabetes (either type 1 or 2), regardless of disease duration, severity, or control, will specifically exclude subjects from eligibility.**

4. Subjects with a cardiac pacemaker, implanted defibrillator or other implanted electronic device.
5. History of prior intraocular or corneal surgery (including cataract extraction), active ophthalmic disease or abnormality (including, but not limited to, symptomatic blepharitis, recurrent corneal erosion, dry eye syndrome, neovascularization > 1 mm from limbus), retinal detachment/repair, clinically significant lens opacity, clinical evidence of trauma, corneal opacity within the central 9 mm and visible on topography, at risk for developing strabismus, or with evidence of glaucoma or propensity for narrow angle glaucoma.

**NOTE: Subjects with open angle glaucoma, regardless of medication regimen or control, or an IOP greater than 21 mmHg at screening, are specifically excluded from eligibility.**

6. Evidence of keratoconus, corneal dystrophy or irregularity, or abnormal topography.
7. Known sensitivity or inappropriate responsiveness to any of the medications used in the postoperative course.
8. Desire to have monovision.
9. Intolerance to multifocal correction based on questionnaire responses to contact lens trial.
10. Participation in any other clinical study.

#### **EVALUATION CRITERIA:**

The purpose of this clinical study is to evaluate the feasibility of a new treatment algorithm to increase depth of focus combined with wavefront guided LASIK correction of myopic refractive errors using the iDesign Advanced Wavescan Studio™ System (software version 1.2) with iDesign 1.3-PRESBY TPS and Star S4 IR™ Excimer Laser System (Abbott Medical Optics, CA). The primary endpoint is mean monocular distance corrected intermediate visual acuity under photopic conditions at 67 cm. Secondary endpoint is mean monocular distance corrected near visual acuity under photopic conditions at 40 cm. Safety endpoints include mean monocular best spectacle corrected distance visual acuity under photopic conditions, induced manifest refractive astigmatism, and serious and device related adverse events.

#### **DATA ANALYSIS:**

The PresbyT-LASIK treatments will be compared to iDesign CustomVue treatments. All endpoints will be evaluated at 6 months. The safety population will be the primary analysis population for all endpoints and includes all eyes that receive study treatment.

#### **STUDY VISITS AND PROCEDURES:**

Inclusion and exclusion qualifications will be assessed at the preoperative visit according to the inclusion/exclusion criteria. The Informed Consent Document and Personal Health Information Protection Act Authorization must be signed by patients who agree to participate in the study prior to undergoing any study-specific procedures. After

determination that all inclusion/exclusion criteria have been met and the informed consent has been signed, subjects will be enrolled in the study. Subjects and study personnel performing the vision testing and refractions will be un-masked for the duration of the study.

The STAR S4 IR™ Excimer Laser System and the iDesign Advanced WaveScan Studio™ System will be used to perform wavefront-guided LASIK treatments. Both eyes of subjects will be treated in the study. Surgery will be performed with iDesign CustomVue treatments on the dominant eye and PresbyT-LASIK treatments on the non-dominant eye. The Dolman test will be utilized for eye dominance determination as described in **Appendix R**.

Key preoperative and postoperative data include iDesign measurements, visual acuities, manifest refraction, keratometry (iDesign and auto/manual), pachymetry, biomicroscopic slit-lamp findings, intraocular pressure, adverse events, ocular visual symptoms and patient reported outcomes (PRO) assessments of visual functioning and visual symptoms (using the PRVSQ for PRK/LASIK instrument). Ocular health and history are also assessed preoperatively. A chart summary of procedures required at each study visit is provided in **Appendix A**.

